#### 10.5.1.4 Other safety data

#### **ECG**

12-lead ECGs including PR, QRS, QT, QTcF, and RR intervals will be obtained for each patient during the study. ECG data will be read and interpreted locally.

Categorical analysis of QT/QTc interval data based on the number of patients meeting or exceeding predefined limits in terms of absolute QT/QTc intervals or changes from baseline will be presented. In addition, a listing of these patients will be produced.

#### Vital signs

Data on vital signs will be tabulated and listed, notable values will be flagged.

Data from other tests (including ECHO, performance status, dermatological evaluation, ) will be listed and summarized using descriptive statistics as appropriate. Notable values may be flagged. Notable/Abnormal values for safety data will be further specified in the SAP and will be used for shift tables. Any other information collected will be listed as appropriate.

Analyses will be performed on the safety set for both study cohorts.

#### 10.5.1.5 Supportive analyses for secondary objectives

Not applicable.

#### 10.5.1.6 Tolerability

Tolerability will be summarized in terms of dose reductions or drug interruption due to an AE.

#### 10.5.1.7 Palatability

Data on palatability assessments (bitterness, sweetness, texture and overall taste) will be summarized and listed.

#### 10.5.2 Pharmacokinetics

The PAS will be used in all pharmacokinetic data analysis and PK summary statistics for each cohort.

#### 10.5.2.1 Non-compartmental Analysis

On Day 15 PK parameters for dabrafenib, its metabolites and trametinib will be calculated with standard non-compartmental methods using Phoenix WinNonlin (Pharsight, Mountain View, California in US). The PK parameters listed in Table 10-1 will be estimated and reported, when feasible as per the SAP.

Table 10-1 Non-compartmental pharmacokinetic parameters

| AUClast | The AUC from time zero to the last measurable concentration sampling time (tlast) (ng*h/mL)  |  |  |
|---------|--|--|--|
| AUCtau  | The AUC calculated to the end of a dosing interval (tau) at steady-state (ng*h/mL); tau= 12 hrs  |  |  |
| Cmax    | The maximum (peak) observed plasma, blood, serum, or other body fluid drug concentration after single dose administration (ng/mL)  |  |  |
| Tmax    | The time to reach maximum (peak) plasma, blood, serum, or other body fluid drug concentration after single dose administration (h)   |  |  |
| Ctrough | Measured concentration at the end of a dosing interval at steady state (taken directly before next administration) (ng/mL)The trough (predose) plasma concentration determined directly from the raw concentration-time data |  |  |

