#### 1.2.2.3 Pharmacokinetics - Trametinib

Trametinib pharmacokinetic (PK) parameters in adults were determined after single and repeat dose oral administration. Trametinib was absorbed rapidly, requiring 1.5 hr to reach the maximum concentration (Tmax) after single oral administration under fasting conditions [MEK113709]. The absolute oral bioavailability of a single trametinib 2 mg tablet is moderate to high (72%) relative to a co-administered intravenous microdose [MEK116540, CTMT212X2101]. Single-dose administration of trametinib with a high-fat, high-calorie meal resulted in a 70% decrease in maximum observed concentration (Cmax) and a 10% decrease in

area under the concentration-time curve from time zero (pre-dose) extrapolated to infinity  $[AUC(0-\infty)]$  compared to fasted conditions [MEK113709].

Following repeat-dosing, the mean area under the concentration-time curve over the dosing interval (AUC0- $\infty$ ) and Cmax increased in a dose proportional manner. Trametinib accumulates with repeat dosing, with a mean accumulation ratio at the recommended dose of 2 mg once daily of 5.97. Terminal half-life is 5.3 days, determined after single dose administration. Steady state is achieved by Day 15, with little difference in pre-dose (trough) concentration at the end of the dosing interval (C $\tau$ ), Cmax and AUC from time zero (pre-dose) to 24 hr AUC(0-24h) between Day 15 and Day 21. In adults receiving trametinib 2 mg daily for 15 days (n=13) the geometric mean AUC(0-24h) (coefficient of variation [CV] %) was 370 (22%) ng\*hr/mL, Cmax 22.2 (28%) ng/mL, Tmax 1.75 hr (range 1-3 hr), and C $\tau$ 12.1 (19%) ng/mL (Infante, 2012).

The oral liquid formulation (0.05 mg/mL) had similar bioavailability to the trametinib tablet formulation. Single dose administration of trametinib as a 2 mg oral solution compared to the oral tablet resulted in a 12%, 10 % and 71% increase in AUC(0- $\infty$ ), AUC(0-last) and Cmax, respectively.

A population PK model was developed with data (n=493) combined from the FTIH study [MEK111054], and the Phase II and III studies in subjects with *BRAF* V600 mutation positive melanoma [MEK113583] and [MEK114267, CTMT212A2301]. Trametinib CL/F was estimated as 5.07 L/hr and was dependent on gender and weight. Although smaller female subjects will tend to have higher exposure than heavier male subjects, no dosage adjustment is warranted in this population.

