#### 6.1.1.1 Dabrafenib (DRB436) and trametinib (TMT212) dosing

Study medications should be taken as follows:

- Dabrafenib will be administered twice daily per the dosing regimen shown in Table 6-1, Table 6-2, Table 6-3 and Table 6-4.
- Trametinib will be administered once daily per the dosing regimen shown in Table 6-5, Table 6-6, Table 6-7 and Table 6-8.
- Trametinib should be taken in combination with dabrafenib once daily, preferably in the morning.
- Dabrafenib capsules and trametinib tablets should be taken with approximately 120-240 mL of water.
- Trametinib pediatric oral solution formulation will be administered with a graduated syringe. Please refer to the trametinib oral solution Instructions for Use.
- Dabrafenib pediatric oral suspension formulation administration will be administered using dosing cup and/or graduated syringe. Please refer to dabrafenib oral suspension Instructions for Use.
- Refer to the dabrafenib and trametinib Instructions for Use documents if enteral feeding tubes are required for administering pediatric oral solutions.
- Patients less than 12 years of age who weigh less than 16 kg must be administered the dabrafenib dispersible tablets for oral suspension.
- Patients equal to or greater than 12 years of age who weigh less than 19 kg must be administered the dabrafenib dispersible tablets for oral suspension.
- Patients less than 6 years old who weigh less than 26 kg must be administered the trametinib oral solution.
- Patients older than 6 years old must weigh at least 33 kg to be administered the trametinib tablets.
- Patients should be encouraged to take dabrafenib at approximately 12 hour intervals and at similar times each day.
- Study treatment should be administered under fasting conditions, at least 1 hour before or 2 hours after a meal.
- If it is not possible for a patient to tolerate the fasting conditions noted above, study treatment may be administered with a small non-fat meal (e.g. small amount of apple juice/sauce, a piece of dry toast). Patients and their guardians should be advised to avoid administering study drug with milk or high-fat, high-calorie foods.
- Patients who are being breastfed may continue to be breastfed on demand. If the patient is breastfed during collection of PK samples the time of breastfeeding should be recorded as a meal.

- If a patient vomits after taking study drug, the patient should be instructed not to retake the dose and wait for the next scheduled dose.

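### Table 10-1 fixes tau at 12 h for the steady-state AUC of every analyte, which fits twice-daily dabrafenib but covers only half of trametinib's once-daily dosing interval

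*Protocol*

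**What the plan says.** Section 10.5.2.1 names the analytes: "On Day 15 PK parameters for dabrafenib, its metabolites and trametinib will be calculated with standard non-compartmental methods". It then says: "The PK parameters listed in Table 10-1 will be estimated and reported, when feasible as per the SAP". Table 10-1 has one AUCtau row, with no split by drug: "The AUC calculated to the end of a dosing interval (tau) at steady-state (ng*h/mL); tau= 12 hrs". The protocol gives no separate tau for trametinib anywhere else.

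The regimens differ. Section 6.1.1.1 states "Dabrafenib will be administered twice daily per the dosing regimen shown in Table 6-1" and, for the second drug, "Trametinib will be administered once daily per the dosing regimen shown in Table 6-5". Sections 2.3 and 6.1.1 agree.

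The background sections respect the difference. The adult dabrafenib reference in section 2.3 is an AUC over 12 h. The adult trametinib reference in section 1.2.2.3 is an AUC over 24 h.

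**The concern.** For trametinib the AUCtau row contradicts itself. It asks for the area to the end of a dosing interval and then stops halfway through one. Followed literally, the study report would carry a trametinib steady-state AUCtau that is not a full-interval exposure and is not comparable with the 24-hour adult value quoted in section 1.2.2.3.

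Characterising trametinib pharmacokinetics is a secondary objective in both cohorts (Table 3-1). For children under 6 years, Table 1-4 shows earlier trametinib data from only three patients, so the exposure summaries from this trial will be read closely. The protocol's preferred trametinib metric is the average concentration, Cavg. Table 10-1 does not list it, but it is an obvious quantity to derive from AUCtau, and an AUCtau over the wrong interval would carry its error into it.

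**Working it through.** **Step 1. Derive tau from each regimen.**
- Dabrafenib, twice daily: 24 h / 2 = 12 h. This reproduces the figure in Table 10-1.
- Trametinib, once daily: 24 h / 1 = 24 h. Table 10-1 has 12 h, so it covers 12/24 = 0.50 of the interval.

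**Step 2. Inputs for the size of the error.** All come from section 1.2.2.3, for adults on 2 mg daily at Day 15: AUC(0-24h) 370 ng*h/mL, Cmax 22.2 ng/mL, Tmax 1.75 h, trough 12.1 ng/mL. The same section gives an adult CL/F of 5.07 L/h.

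**Step 3. Check that 370 is a full-interval value.** At steady state, dose / (CL/F) = 2 mg / 5.07 L/h = 394 ng*h/mL per 24 h. The reported 370 is within about 7% of this, so it is a full-day exposure.

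**Step 4. Bound the 12-hour area.**
- Upper bound: if the trough is the lowest concentration, hours 12 to 24 contribute at least 12 x 12.1 = 145.2. AUC(0-12) is then at most 370 - 145.2 = 224.8 ng*h/mL, or 224.8/370 = 61% of the full value.
- Lower bound: if the first 12 h carry at least as much exposure as the second 12 h, AUC(0-12) is at least 370/2 = 185 ng*h/mL, or 50%.

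The shortfall is therefore 39-50%.

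**Step 5. An illustrative point value.** Assume a linear rise from 12.1 to 22.2 ng/mL over 1.75 h, with area (12.1 + 22.2)/2 x 1.75 = 30.0. After that, assume an exponential-plus-constant fall back to 12.1 at 24 h. Choosing the rate so that the total is 370 gives 0.109 per hour and AUC(0-12) = 212 ng*h/mL. That is 57% of the full value, a shortfall of about 43%, inside the bounds.

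**Step 6. Knock-on effect on Cavg, if it were derived from AUCtau.** The correct value for this profile is 370/24 = 15.4 ng/mL.
- AUC(0-12) divided by 24: 185/24 = 7.7 to 224.8/24 = 9.4 ng/mL, too low.
- AUC(0-12) divided by 12: 185/12 = 15.4 to 224.8/12 = 18.7 ng/mL, equal or too high.

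The direction depends on the divisor, and the protocol does not state one.

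**Step 7. What the sampling supports.** In Table 7-6 the last Week 3 Day 1 (Day 15) post-dose sample is at 8 h. In patients under 10 kg, the Day 15 samples are pre-dose, 2 h and 4 h only. A 24-hour trametinib area therefore leaves 24 - 8 = 16 h without a sample, or 24 - 4 = 20 h in the smallest children. A 12-hour area also runs past the last sample. At steady state, however, the pre-dose sample is one full dosing interval after the previous trametinib dose, so it can stand for the 24-hour concentration. No scheduled trametinib sample plays that part at 12 h.

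**The case against.** The case for leaving this alone has four parts.

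- **The table is qualified by feasibility under the SAP, and the SAP is not among the documents at hand.** This lets a parameter be dropped where it cannot be estimated. It does not correct a tau that the protocol prints.
- **The consequences are limited.** This stands. A reader might infer that the plan would show children to be underexposed against adults, or that it undermines the trametinib dose rationale. The documents do not support that. Section 2.3 rests the trametinib dose on safety, tolerability and Cavg above 10 ng/mL, and section 1.2.2.3 compares children with adults on Cavg and Ctrough. The adult 24-hour AUC is background, and sections 10.5.2.1 to 10.5.2.3 plan no comparison of AUCtau with adults and no test or decision based on it. A reader might also infer that Cavg would be halved. That needs division by 24, a formula the protocol does not give.
- **Changing 12 to 24 is not enough.** This also stands. The unsampled hours need a rule, and section 10.5.2.3 says missing concentrations are not imputed.
- **The Cmax and Tmax rows also look wrong, because they refer to single-dose administration.** That wording is generic, and the sentence introducing the table fixes Day 15. No calculated value changes, so it is editorial and adds nothing to the AUCtau point.

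**Conclusion.** The point holds for one parameter and one drug. As written, trametinib AUCtau at steady state would cover half the dosing interval and come out about 39-50% below the full-interval value. The AUCtau definition is correct for dabrafenib and its metabolites.

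The range rests on treating adult geometric means from 13 patients as one profile, on the trough being the lowest concentration, and on the first half of the interval carrying at least half the exposure. Paediatric profiles may differ in shape, so the percentage is indicative. The mismatch between 12 h and once-daily dosing does not depend on it.

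This is an error in a descriptive secondary analysis. It touches no efficacy endpoint, hypothesis test, sample size or stopping rule, and it says nothing about whether any dose is right. It is still worth correcting, because it is a stated analysis rule that gives the wrong quantity under the right label.

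**What to change.** In Table 10-1, give tau by analyte: 12 h for dabrafenib and its metabolites, 24 h for trametinib. Then add a short rule to section 10.5.2.1, cross-referenced from section 10.5.2.3, stating that:

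- the steady-state pre-dose concentration serves as the end-of-interval value for trametinib;
- this use of an observed sample is not imputation of a missing concentration;
- trametinib AUCtau is reported only where the profile supports it. This matters most for patients under 10 kg and for LGG patients on the sparse schedule in Table 7-7.

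The single-dose wording in the Cmax and Tmax rows can be tidied in the same edit.

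The cost is a few lines of text, with no new samples and no change to dosing. The downside is that the trametinib area would rely on a steady-state assumption for the unsampled 16 h (20 h in the smallest children). Section 1.2.2.3 supports that assumption in adults by reporting steady state by Day 15. It is weaker in a patient whose doses were missed, vomited or interrupted shortly before sampling, so the steady-state validity check already planned in section 10.5.2.2 should be applied before the pre-dose value is used this way.

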#### 10.5.2.2 Basic table, figure and listing

[figure not shown]
Validity of PK samples will be confirmed by checking sampling time window, steady state condition and occurrence of vomiting with respect to time of dose. Only confirmed PK concentrations will be used in the analyses.

Summary statistics of plasma concentration of dabrafenib, its relevant metabolites and trametinib will be reported by visit and actual leading dose (i.e. the dose taken on the day prior to the PK sampling day) for all patients that provided at least one evaluable PK sample. Summary statistics include n, arithmetic mean, median, SD, geometric mean, coefficient of variation (CV) (%) and geometric CV (%), minimum and maximum. Zero concentrations will not be included in the geometric mean calculation Graphical presentation will be provided on mean concentration at each scheduled time point for PK sub-population where the full PK profile is available.

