#### 1.2.1.3 Pharmacokinetics - Dabrafenib

In adults following oral administration of dabrafenib HPMC capsules, the plasma concentrations of dabrafenib peaked approximately 2 hours post-dose and decreased thereafter following a bi-exponential decline. The terminal half-life (t1/2) is 8.4 hours, mainly due to a prolonged terminal phase after oral administration. The t1/2 following IV microdose is 2.6 hours.

Increases in maximum observed concentration (Cmax) and area under the concentration time curve (AUC) were generally dose-proportional with single doses and less than dose proportional after repeat BID dosing. Following administration of 150 mg BID, the AUC on Day 18 was 27% lower than on Day 1. Following administration of 150 mg BID (HPMC capsules), the geometric mean Cmax, AUC(0- $\tau$ ) and predose concentration (C $\tau$ ) were 1478 ng/mL, 4341 ng\*hr/mL and 26.1 ng/mL, respectively. Interpatient variability was 37-38% for Cmax and AUC(0- $\tau$ ) and 119% for C $\tau$ . Administration of dabrafenib with food reduced the bioavailability (Cmax and AUC decreased by 51% and 31% respectively) and delayed the absorption of dabrafenib capsules when compared to the fasted state. Dabrafenib should be taken either at least one hour before, or at least two hours after a meal.

The relative bioavailability of single dose dabrafenib was slightly lower (AUC decreased by 20%) when administered as an oral suspension (dispersible tablets) compared to HPMC capsules. This difference in AUC is not considered clinically relevant based on the exposure-response relationship in adult melanoma and therefore no dose adjustment will be made for the dispersible tablets in this study.

Results of a population pharmacokinetic analysis in adults indicated that body weight is a significant predictor of oral clearance and apparent volume of distribution for dabrafenib, with higher weight being associated with higher clearance and lower plasma concentrations; however this does not appear to have a clinically relevant effect on exposure. The range of body weights of patients included in the population PK analysis was 36 to 150 kg. Dabrafenib apparent oral clearance and apparent volume of distribution were predicted in a typical adult patient with low (50 kg) or high (140 kg) body weight and were shown to be within 20% of the value of a typical 80 kg patient. This difference was not considered clinically relevant.

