**Novartis** 

#### 7.2.3 **Pharmacokinetics**

Pharmacokinetic blood samples will be collected for the analysis of plasma concentrations of dabrafenib. metabolites hydroxy-dabrafenib, carboxy-dabrafenib, and desmethyldabrafenib (GSK2285403, GSK2298683 and GSK2167542, respectively), and trametinib.

Full PK blood samples will be collected as described in Table 7-6 for all patients in the HGG cohort and the first 20 LGG patients randomized to dabrafenib plus trametinib treatment. For the remaining LGG patients on dabrafenib plus trametinib treatment, sparse PK blood samples will be collected as described in Table 7-7. An unscheduled PK blood sample may be collected at any time for measurement of plasma drug concentrations if clinically indicated or at the Investigator's discretion. PK samples will not be collected from LGG patients after they crossover from carboplatin with vincristine treatment.

The date and exact time of dosing, as well as the date and actual time of blood sampling must be recorded on the appropriate eCRF pages. Any sampling problems (e.g., patient took study drug before blood sample, scheduled sampling time is missed, sample is not drawn according to the schedule) should be noted as a comment on the eCRF.

If vomiting occurs during the course of treatment, no re-dosing of the patient is allowed, and medication should resume at the next scheduled dose. The occurrence and frequency of any vomiting must be noted in the adverse events section of the eCRF. In addition, the date and exact time of vomiting should only be recorded if it occurs within 4 hours of dosing on the days of full PK sampling. If a vomiting episode occurs within the first 4 hours post-dosing during the day of the last dose prior to trough PK samples the exact time (whenever possible) must be noted on the PK Dose and Administration Record eCRF

Concentrations of dabrafenib, its metabolites and trametinib will be summarized; a detailed description of the planned PK analyses is given in Section 10.5.2.

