### 7.2.3.2 Analytical method

Plasma concentrations of dabrafenib and its metabolites hydroxy-dabrafenib (GSK2285403), carboxy-dabrafenib (GSK2298683), and desmethyl-dabrafenib (GSK2167542) and trametinib will be measured using validated liquid chromatography/mass spectrometry/ mass spectrometry (LC/MS/MS) methods. The lower limit of quantification (LLOQ) for dabrafenib, hydroxy-dabrafenib and desmethyl-dabrafenib is 1 ng/mL and 0.25 ng/mL for trametinib for a 50  $\mu$ L aliquot of human plasma. The LLOQ for carboxy-dabrafenib is 5 ng/mL for a 25  $\mu$ L aliquot of human plasma. Concentrations below the LLOQ will be treated as zero.

Meal records must be kept for all patients on PK days as indicated in Table 7-1. The date, start and end time, and percentage consumed for all meals on PK days must be recorded in the CRFs.

[figure not shown]
<sup>b The first Dose Reference ID (DRID no.) is for current dose, while the second DRID no. is for the last dose the patient received prior to the collection of the PK sample.

<sup>c Unscheduled PK samples will be uniquely, sequentially numbered 2001, 2002, etc.

<sup>d Last dose the patient received prior to the collection of the unscheduled PK

e PK samples can be collected anytime between 1-3 hours after the morning dose

f PK samples can be collected anytime between 5-10 hours after the morning dose

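### For sparse-PK patients, the vomiting check on the Week 3 post-dose samples needs times that the protocol tells sites not to record

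*Protocol*

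**What the plan says.** Protocol Section 10.5.2.2 sets the rule for admitting PK samples: "Validity of PK samples will be confirmed by checking sampling time window, steady state condition and occurrence of vomiting with respect to time of dose". It adds that "Only confirmed PK concentrations will be used in the analyses". The rule is not limited to full profiles. The same section summarises concentrations for every patient with at least one evaluable sample.

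Section 7.2.3 says what sites record. Occurrence and frequency of any vomiting go into the adverse event pages. For timing, it says: "date and exact time of vomiting should only be recorded if it occurs within 4 hours of dosing on the days of full PK sampling". A further sentence, beginning "If a vomiting episode occurs within the first 4 hours post-dosing during the day of the last dose prior to trough PK samples", asks for the exact time where possible and is not restricted to full sampling. The section also rules out re-dosing after vomiting.

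Full sampling (Table 7-6) applies to all high-grade glioma (HGG) patients and to the first 20 LGG patients randomized to dabrafenib plus trametinib. The remaining LGG patients on that arm follow the sparse schedule (Table 7-7). It has a pre-dose sample in Week 3, two post-dose windows on the same day (1–3 h and 5–10 h), and a pre-dose sample in Week 4. Which of these a child gives depends on body weight.

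**The concern.** A check of vomiting against time of dose needs a time of vomiting. On a sparse-PK day the protocol tells the site not to record one. Suppose a child vomits the Week 3 morning dose soon after taking it. The dose is not repeated, and the samples in the 1–3 h and 5–10 h windows may then reflect a dose that was largely lost. The analyst has no recorded time from which to see this.

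Two outcomes are possible, and the protocol does not choose between them. The sample may be kept, and a falsely low concentration enters the summaries. Or every sample from a day with reported vomiting may be dropped, including those where the child vomited in the evening after sampling was over. Either way the stated validation is not what is done. A later SAP cannot repair this, because the gap is in data collection.

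**Working it through.** No design figure in the plan is at issue, so the check sets the sections side by side and counts the samples.

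**Is there another route to the time?**

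- *Full-PK rule (Section 7.2.3).* It does not apply, because the sparse schedule is a separate log (Table 7-7).
- *Trough rule (Section 7.2.3).* It covers the day of the last dose before each trough, so both sparse pre-dose samples (Weeks 3 and 4) are covered. The post-dose samples come from the Week 3 Day 1 morning dose. That dose is given after the Week 3 trough is drawn and about a week before the Week 4 trough. It is not the last dose before either.
- *Adverse event pages (Section 8.1.1).* Duration is recorded as start and end dates. A date cannot tell vomiting 30 minutes after the dose from vomiting that evening.

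None of the three gives a required time for the sparse post-dose samples.

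**How many patients?** Inputs: 102 LGG patients randomized 2:1 (Section 10.8.2), and the first 20 on dabrafenib plus trametinib fully sampled (Section 7.2.3).

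- LGG patients on dabrafenib plus trametinib: 102 × 2/3 = 68
- On the sparse schedule: 68 − 20 = 48, or 48/68 = 71% of that arm
- Among all planned PK patients, with 40 HGG patients: 48/(40 + 68) = 48/108 = 44%

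**How many samples per patient?** (Table 7-7)

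| Weight | Scheduled sparse samples | Post-dose samples without a vomiting time |
|---|---|---|
| ≥25 kg | 4 | 2 (1–3 h and 5–10 h) |
| 10 to <25 kg | 3 | 1 (5–10 h only) |
| <10 kg | 2 | 0 |

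The documents give no weight distribution. The total therefore lies between 0 (all under 10 kg) and 48 × 2 = 96 (all at 25 kg or more). If all were 10 to under 25 kg, it would be 48.

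**Is it still correctable at this amendment?** At Amendment 5, 44 LGG patients had been randomized. At 2:1 that is about 44 × 2/3 ≈ 29 on dabrafenib plus trametinib, so the 20 full-PK places were probably filled. Of the 102 − 44 = 58 still to come, about 58 × 2/3 ≈ 39 would be on that arm, all on the sparse schedule. These are expected numbers, not counts.

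**The case against.** The strongest reply is that the check can be done well enough without a mandated time. All vomiting is reported with dates. On PK days the dose is taken in the clinic under supervision (Section 6.1.1.2), and exact dosing and sampling times are recorded. Sampling problems are to be noted as eCRF comments (Section 7.2.3). A child who vomits within half an hour is probably still on site, and vomiting dated to the PK day can be flagged. Nothing says that a sample with unknown vomiting time passes by default.

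Much of this stands. The gap does not extend to sparse troughs, it is absent in the smallest children, and acceptance of bad samples is a possibility rather than a stated rule. It does not close the gap, though. A flag by date cannot order vomiting against the dose, and a voluntary comment is weak when the instruction is to record the time only on full-PK days.

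A reader might go further and infer that fed samples are also wrongly accepted, because meal records are collected and food is not among the three checks. The protocol does not support that. Section 10.1.5 leaves the definition of an evaluable sample to the SAP, and Section 6.1.1.1 permits a small non-fat meal and breastfeeding, so a fed sample is not invalid by the protocol's own rule. Nor does it help to apply the 31% food effect to a paediatric mean AUC of about 3975 ng·h/mL (3975 × 0.69 ≈ 2743) and compare the result with 3599. That assumes every child is fed with the full adult capsule effect, and 3599 is a lower confidence limit for an adult mean.

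**Conclusion.** The point holds in a narrow form. Sections 7.2.3 and 10.5.2.2 do not fit together for the Week 3 post-dose samples of sparse-PK patients: planned for about 48 of 68 LGG patients on dabrafenib plus trametinib, with at most two samples each. The count assumes that randomization reaches 102 at exactly 2:1 and that 20 patients are fully sampled.

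The size of any bias cannot be derived. A reader might take the 71%, or the 42% vomiting rate in Section 1.2.3.1, to mean that most LGG patients are affected. The first is the share assigned to sparse sampling. The second is any vomiting among 12 children with a median of 41 weeks of treatment. Neither is the chance of losing one particular morning dose, for which the documents give no figure.

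The consequence is confined to secondary PK summaries. The primary endpoint is untouched. The change is worth making because the stated check cannot otherwise be done and the times cannot be reliably recovered afterwards.

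**What to change.** In Section 7.2.3, delete 'full' from the sentence on recording vomiting times, so that vomiting within 4 hours of dosing is dated and timed on every PK sampling day, full or sparse. Open the corresponding eCRF field for sparse-PK patients. Section 10.5.2.2 can then stand as written.

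The cost is one word in the protocol and one extra eCRF entry for a sparse-PK patient who vomits within the window. No extra blood sample or visit is needed. Sparse samples taken before the change would still lack a required time.
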